INVESTIGATOR STUDY PLAN- REQUIRED

Study Protocol

An open-label, feasibility trial of adjunctive telmisartan in patients with treatment resistant schizophrenia

[name], MPH

Identifier: NCT03868839

Document Date: 06/11/2018

A. BACKGROUND

1. Treatment resistant schizophrenia (TRS): TRS, which affects approximately 1/3 of patients with schizophrenia (Meltzer 1997). Currently available antipsychotic agents all fall into the “D2, me too” category. However, the abnormal presynaptic dopamine transmission usually seen in schizophrenia are absent in TRS (Demjaha et al 2012). Novel treatment approaches targeting alternative neural circuits or pathways are urgently needed.

Increased glutamate levels have been reported in antipsychotic-naïve or free patients with schizophrenia (de la Fuente-Sandoval et al 2013, Kraguljac et al 2013). Some studies suggested that antipsychotic treatment may reduce brain glutamate to the levels similar as in healthy controls (de la Fuente-Sandoval et al 2013, Kegeles et al 2012). However, recent studies found higher glutamate levels in the anterior cingulate cortex of antipsychotic-treated first episode patients with unremitted psychotic symptoms, and in treatment-resistant patients than in medication responders (Demjaha et al 2014, Egerton et al 2012). Abnormal glutamatergic signaling secondary to excessive stimulation of non-NMDA glutamate receptors (i.e., AMPA and kainate) may result in calcium influx and neuronal injury, which likely lead to clinical symptoms including cognitive impairment in patients with schizophrenia (Deutsch et al 2001).

3. Telmisartan, inflammation and oxidative stress: Studies have demonstrated that blockade of AT1R by telmisartan reduces inflammation, apoptosis, and oxidative stress (Jung et al 2007, Sato et al 2014). In addition, telmisartan activates the nuclear receptor peroxisome proliferator-activated receptor γ (PPAR γ), which regulates multiple pathways to counteract inflammation and oxidative stress, and promote neuroprotection (Min et al 2012, Pang et al 2012).

4. Potential benefit of telmisartan in schizophrenia: We recently reported that adjunctive treatment with telmisartan improves schizophrenia symptoms (Fan et al 2017). We now further propose to examine whether telmisartan targets glutamatergic signaling in the brain with neuroimaging to measure concentrations of cerebral glutamate metabolites in patients with TRS.

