We propose a 4-week, open-label, feasibility trial of adjunctive telmisartan in adult patients with TRS. We plan to recruit 10 patients. All patients will receive telmisartan 80mg daily for 4 weeks.

B. SPECIFIC AIMS

Primary

1. Evaluate changes in blood biomarkers for inflammation and oxidative stress.

C. STUDY DESIGN

Screening visit: After signing a HIPAA compliant informed consent form, subjects will undergo a review of medical history and concomitant medications, and a physical exam. The MINI International Neuropsychiatric Interview will be performed to confirm the psychiatric diagnosis. Subjects will also have a urine drug screen, urine pregnancy test, a complete blood count (CBC), complete metabolic panel (CMP), vital signs, 12-lead ECG.

Baseline visit: After the screening visit, eligible subjects will undergo: 1) vital signs; 2) efficacy assessment battery; 3) safety assessment battery; 4) blood biomarkers for inflammation and oxidative stress, including glutathione (GSH), glutathione disulfide (GSSG), high sensitivity C reactive protein (hsCRP), interleukin 6 (IL-6) and tumor necrosis factor α (TNF α).

Week 1, 2, 3 visits: Vital signs will be assessed. Treatment compliance and possible adverse effects will be evaluated. Subjects will receive one week supply of study medication. Urine drug screen will be repeated at week 2 only.

Week 4 visit: Subjects will undergo: 1) vital signs; 2) efficacy assessment battery; 3) safety assessment battery; 4) blood biomarkers for inflammation and oxidative stress, including GSH, GSSG, hsCRP, IL-6 and TNF α . Lab samples for CBC and CMP will also be collected.

Early termination visit: Subjects will undergo: 1) vital signs; 2) safety assessment battery; 3) CBC and CMP.

D. STUDY POPULATION

Subject eligibility

Inclusion Criteria

Each subject must meet all of the following criteria to be eligible for this study:

1. Age 18-65 years inclusive.
2. Primary diagnosis of Schizophrenia established by a structured psychiatric evaluation (MINI) based on Diagnostic and Statistical Manual of Mental Disorders Fifth Edition (DSM-V) criteria.
3. A Positive and Negative Syndrome Scale (PANSS) (Kay et al 1987) total score ≥ 70 with a score of ≥ 4 on two or more of the following PANSS items: delusions, conceptual disorganization, hallucinatory behavior, suspiciousness, and unusual thought content.
4. A score of ≥ 4 on the Clinical Global Impression—Severity (CGI-S) (Guy, 1976).

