Complete blood count (CBC): White blood cell (WBC) count with differential (absolute neutrophil count, lymphocytes, monocytes, basophils, and eosinophils), red blood cell (RBC) count, hemoglobin (Hgb), hematocrit (Hct), and platelet count.

Comprehensive metabolic panel (CMP): glucose, sodium, potassium, calcium, chloride, carbon dioxide, blood urea nitrogen (BUN), creatinine, calculated glomerular filtration rate, uric acid, phosphorus, magnesium, total protein, albumin, aspartate amino transferase (AST), alanine amino transferase (ALT), alkaline phosphatase (ALP), total bilirubin.

Blood levels of GSH, GSSG, hsCRP, IL-6, TNF α : Blood samples for GSH, GSSG, hsCRP, IL6 and TNF-alpha will be run at the UMass Memorial labs.

The PI, or medically qualified designee, should mark either “CS” for Clinically Significant or “NCS” for Not Clinically Significant in the margin of the laboratory result source document for items outside the normal range.

Urine drug screen: The test includes the following substances: opioids, cocaine, amphetamines, methadone, cannabinoids, barbiturates, benzodiazepines, methamphetamine, and phencyclidine.

Urine pregnancy test: The test will be performed in female subjects of childbearing potential using a dipstick urine test during the screening visit.

12-Lead Electrocardiogram (EGG)

A 12-lead ECG will be taken at following a supine rest for 5 minutes. The ECGs will be reviewed by the PI or medically qualified designee, and a cardiologist to assess any immediate abnormalities. The findings of the ECGs will be marked as normal, abnormal-not clinically significant, or abnormal-clinically significant.

Psychiatric diagnostic assessment

Mini International Neuropsychiatric Interview (MINI v7.0): The MINI 7.0 is a short clinician administered structured diagnostic interview for major psychiatric diagnoses in DSM-5 with an administration of around 20 minutes.

Efficacy assessment battery

The Positive and Negative Syndrome Scale (PANSS) (KAY ET AL 1987): The PANSS will be used to measure symptom severity in this trial. The PANSS is a 30-item questionnaire used to evaluate schizophrenia symptoms, based on the clinical interview as well as reports of family members or primary care hospital workers. The PANSS consists of Positive Symptom subscale (7 items), Negative Symptom subscale (7 items), and General Psychopathology subscale (16 items). Each item is scored on a 7-point scale with higher scores representing increasing levels

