of psychopathology: 1) Absent, 2) Minimal, 3) Mild, 4) Moderate, 5) Moderate severe, 6) Severe, and 7) Extreme.

Scale for Assessment of Negative Symptoms (SANS) (Andreasen 1989): The SANS assesses 5 domains: affective flattening, alogia, avolition/apathy, anhedonia/asociality, and attention. Within each domain, separate symptoms are related from 0 (absent) to 5 (severe).

Clinical Global Impressions–Severity (CGI-S) and Clinical Global Impressions–Improvement (CGI-I) Scales (Guy, 1976): The CGI-S is an observer-rated scale that measures illness severity. The severity is measured using a 7 point Likert scale: 1) Normal, not at all ill, 2) Borderline mentally ill, 3) Mildly ill, 4) Moderately ill, 5) Markedly ill, 6) Severely ill, and 7) Among the most extremely ill patient. The CGI-I is an observer-rated scale that measures illness improvement. Improvement is measured using a 7 point Likert scale: 1) Very much improved, 2) Much improved, 3) Minimally improved, 4) No change 5) Minimally worse, 6) Much worse, 7) Very much worse.

Safety assessment battery

Adverse Events (AE): Adverse events will be monitored at each study visit. The PI or medically qualified designee will review adverse events at every study visit. AE information is collected and recorded starting on the day the consent is signed until the end of an individual’s participation in the study.

The Columbia Suicide Severity Rating Scale (C-SSRS) (Posner et al 2007): The C-SSRS is a low-burden measure of the spectrum of suicidal ideation and behavior that was developed in the National Institute of Mental Health Treatment of Adolescent Suicide Attempters Study to assess severity and track suicidal events through any treatment. It is a clinical interview providing a summary of both ideation and behavior that can be administered during any evaluation or risk assessment to identify the level and type of suicidality present. The C-SSRS can also be used during treatment to monitor for clinical worsening. The C-SSRS will be performed to assess suicidal ideation and behavior. It contains a 1-to-5 rating scale for suicidal ideation of increasing severity (from a “wish list to die” to an “active thought of killing oneself with plan and intent”). The time frame is the past six months for the Baseline/Screening scale and since the last visit for the Since Last Visit scale.

Monitoring and Reporting of Adverse Events

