If a patient discontinues from the study before randomization, then no further follow-up will be expected. However, if the patient discontinues after randomization, but before receiving any study treatment, the patient will be asked to return for a final study visit, during which the procedures outlined in the early termination visit procedures will be completed, including AEs and concomitant medication assessments.

If a patient discontinues from the study before completion and has received the dose of study drug, the patient will be asked to return for a final study visit, at which the procedures outlined in the early termination visit will be completed. Every effort will be made to follow up with patients who discontinue from the study. If the patient refuses follow-up, the reason for the refusal and last contact date should be documented in the CRF.

G. ETHICAL CONSIDERATION

Informed consent

The investigator must ensure that patients are clearly and fully informed about the purpose, potential risks, and other critical issues regarding clinical trials in which they volunteer to participate.

All subjects will receive the consent form for the study. Any questions, concerns, or ambiguities will be clarified by the PI or medically qualified designee prior to the patient signing consent. Subjects will sign informed consent and only then will begin participation in the study.

IRB review

Before study initiation, the investigator will have written and dated approval from the UMass IRB for the protocol, consent form, patient recruitment materials and process (e.g., advertisements), and any other written information to be provided to subjects.

The investigator will provide the IRB with reports, updates, and other information (e.g., safety updates, amendments) according to regulatory requirements and institution procedures.

H. DATA ANALYSIS

There are no published data yet about the effect of telmisartan treatment on the levels of glutamate and GABA in the brain in patients with schizophrenia. The study is intended to provide preliminary evidence of target engagement in the brain, as well as an indication of effect size for the purpose of designing future studies. Paired sample t tests will be used to examine the difference in outcome measures between week 4 and baseline. In addition, Pearson correlation analysis or partial correlation analysis will be used to examine the relationship between changes in biomarkers and changes in symptom outcome measures.

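### Section H gives brain target engagement as a purpose of the study, but no brain measure is scheduled; the only biomarkers collected are five blood analytes

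*Protocol*

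**What the plan says.** Two places in the Protocol present this as a study of the brain.

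- Section H (Data Analysis) opens by noting the lack of published data on brain glutamate and GABA under telmisartan. It then gives the first purpose: "The study is intended to provide preliminary evidence of target engagement in the brain". The second purpose is an effect-size estimate to help plan later trials.
- Section A (Background), item 4, proposes to examine whether "telmisartan targets glutamatergic signaling in the brain with neuroimaging to measure concentrations of cerebral glutamate metabolites in patients with TRS".

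The rest of the plan is about blood and clinical ratings.

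- Section B lists one aim, under Primary: "Evaluate changes in blood biomarkers for inflammation and oxidative stress".
- Section C gives the same four numbered items at baseline and at week 4: "1) vital signs; 2) efficacy assessment battery; 3) safety assessment battery; 4) blood biomarkers for inflammation and oxidative stress".
- Section E describes one set of biomarker assays: "Blood samples for GSH, GSSG, hsCRP, IL6 and TNF-alpha will be run at the UMass Memorial labs".
- Section H plans paired t tests of week 4 against baseline, and correlations for the "relationship between changes in biomarkers and changes in symptom outcome measures".
- The SAP repeats the visit descriptions. Its analysis text is a single sentence reporting a paired t-test, with no outcome named.

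**The concern.** Section H is where the reader learns what the data are meant to show, and the first of its two purposes has no measurement behind it. The word biomarkers in the planned correlations can, on the schedule as written, refer only to blood analytes. Nothing in the documents sets these up as a substitute for brain glutamate or GABA. Under the present wording, a fall in IL-6 or a shift in glutathione could be presented as brain target engagement, and a null result as its absence. Neither reading would be supported. The study is also meant to inform the design of later trials, so it should be clear which quantity its effect sizes describe.

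**Working it through.** No formula applies, and the plan gives no figure on this point to reproduce. The check sets the stated purpose against every place where a measurement would have to appear.

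| Place | What is there | Brain measures |
|---|---|---|
| Protocol B, Specific Aims | One aim, on blood markers | 0 |
| Protocol C, Baseline | 4 numbered items | 0 |
| Protocol C, Weeks 1 to 3 | Vital signs, compliance, adverse effects, drug supply; urine drug screen at week 2 | 0 |
| Protocol C, Week 4 | 4 numbered items, plus CBC and CMP | 0 |
| Protocol C, Early termination | 3 numbered items | 0 |
| Protocol E | 8 assessment headings: medical history, physical exam, vital signs, laboratory assays, ECG, psychiatric diagnosis, efficacy battery, safety battery | 0 |
| Schedule of Events | 17 rows | 0 |
| SAP, Procedures and Statistical Analysis | Same visits; one sentence of analysis | 0 |

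The screening visit adds history, examination, MINI, urine tests, CBC, CMP, vital signs and a 12-lead ECG; none measures the brain. None of the 14 exclusion criteria concerns suitability for imaging.

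**What can be differenced between baseline and week 4.** Blood analytes: GSH, GSSG, hsCRP, IL-6, TNF-alpha = 5. Symptom scales: PANSS, SANS, CGI-S = 3. Total 5 + 3 = 8, none of them a brain measure. CGI-I is left out although it shares a schedule row with CGI-S: "The CGI-I is an observer-rated scale that measures illness improvement", so it has no baseline value to subtract. Safety items (vital signs, adverse events, C-SSRS, CBC and CMP) are not counted.

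**Could lost text explain the gap?** Some Background text does seem to be missing from the copy reviewed. Its numbering goes from 1 to 3, and four listed references are cited nowhere in the visible text; all four concern the brain (central angiotensin II responses, brain penetration by PET, inflammatory brain disorders, glutamate-induced neurotoxicity). What the Background says about imaging is therefore known only in part. But the Baseline and Week 4 lists run from 1) to 4) unbroken in both documents, and Section E, the schedule and the SAP name the same five analytes. A scheduled scan would have to have dropped out of all of these places at once.

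**The case against.** The strongest reply is that this is a matter of wording. The conflict lies in Background item 4 and one clause of Section H. No planned test, estimate or participant procedure depends on that clause, and no passage calls the blood markers evidence of brain engagement; Sections B and C describe them as markers of inflammation and oxidative stress. This is fair as to scale: the trial is not invalidated and its listed aim is unaffected. But the clause is the analysis section's own statement of what the study is for, and item 4 is phrased as a proposal for this study, so neither can be set aside as general rationale.

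Section B may also be incomplete. It has a plural heading and a Primary subheading with one entry, yet symptom scales are collected and correlations planned. That weakens any argument from the single aim. It does not touch the main point, because a lost aim would still have no visit, procedure or schedule row to serve it.

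Finally, the SAP is partly in the past tense while the Protocol looks forward, and both carry the same date. If the study has already been run, adding imaging may no longer be possible. This bears on which remedy is practical, not on whether the contradiction exists.

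A caution on what remains: ten patients are planned, and neither the blood markers nor PANSS and SANS are collected at early termination. Saying that effect sizes can be obtained is no claim about their precision.

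**Conclusion.** The concern holds, with high confidence. The plan states a purpose of preliminary evidence for brain target engagement and schedules no brain measure: 0 of 17 schedule rows, 0 of 8 Section E assessment headings, and 0 of 4 numbered items at each of baseline and week 4. That purpose cannot be met as written. The blood-marker aim, and effect sizes for the five analytes and three scales, remain within reach.

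The conclusion rests on the visits, Section E, the schedule and the SAP being complete in the copy reviewed, which their mutual agreement supports. It does not rest on the Background or on Section B being complete. This is an internal inconsistency that should be fixed before results are reported.

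**What to change.** **If imaging is not part of this study**, amend two passages by dated amendment.

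- Section H: replace the brain clause with wording such as: *The study is intended to give preliminary evidence of change in blood markers of inflammation and oxidative stress and of its relation to symptom change, with effect sizes for those measures. No brain measure is taken, and these results will not be reported as direct evidence for or against target engagement in the brain.*
- Background item 4: bring it into line, for example by placing neuroimaging among later work.

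The cost is a less ambitious stated purpose and one amendment. No visit, procedure or planned test changes. If conduct is already complete, the same limitation belongs in the study report.

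**If imaging is part of this study**, add it consistently to the aims, visits, Section E, Schedule of Events, Section H and SAP, with the measure, time points and analysis specified. This costs much more: the scans themselves, amendments to both documents and IRB review. It is open only if participants can still be imaged at baseline and week 4.

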Statistical Analysis Plan

(SAP)

An open-label, feasibility trial of adjunctive telmisartan in patients with treatment resistant schizophrenia

[name], MPH

Identifier: NCT03868839

Document Date: 06/11/2018

Participants

Adult outpatients with schizophrenia were recruited from the UMass Memorial Healthcare System in Central Massachusetts. Psychiatric diagnosis was determined using the structured psychiatric evaluation (MINI) based on Diagnostic and Statistical Manual of Mental Disorders Fifth Edition (DSM-V) criteria. Other inclusion criteria included: 1) age 18-65 years; 2) A Positive and Negative Syndrome Scale (PANSS) (Kay et al 1987) total score ≥ 70 with a score of ≥ 4 on two or more of the following PANSS items: delusions, conceptual disorganization, hallucinatory behavior, suspiciousness, and unusual thought content; 3) A score of ≥ 4 on the Clinical Global Impression—Severity (CGI-S) (Guy, 1976); 4) Must have ongoing antipsychotic treatment for at least 8 weeks, with a stable dose for at least 4 weeks. Subjects who have failed to achieve clinically recognized symptom reduction to at least 1 marketed antipsychotic agent, given at a Physician Desk Reference (PDR)-defined therapeutic dose for ≥ 8 weeks during the past 12 months, will be eligible; 5) Female subjects of childbearing potential must have a negative pregnancy test performed at screening visit prior to randomization. Female subjects enrolled in this trial must use adequate birth control; 6) Understands and is able, willing, and (in the opinion of the investigator) likely to fully comply with the study procedures and restrictions. Exclusion criteria were: 1) Psychiatrically unstable; 2) Current insulin treatment for diabetes; 3) Subjects with any clinically significant abnormalities as determined by medical history, physical exam, clinical and lab evaluation suggestive of an underlying disease state that may, in the opinion of the investigator, confound the results of study, increase risk to the subject, or lead to difficulty complying with the protocol; 4) History of immunosuppression; 5) Current or recent radiation or chemotherapy treatment for cancer; 6) Chronic use of steroids (except local use or inhaler); 7) Pregnancy or breastfeeding; 8) Use of diuretics, ACE inhibitors, spironolactone, potassium supplements, digoxin or warfarin because of the possible drug-drug interaction with telmisartan; 9) Tested positive for the urine drug screen. The study was approved by the institutional review board of the University of Massachusetts Medical School and followed the Good Clinical Practice guideline.

Procedures:

Screening visit: After signing a HIPAA compliant informed consent form, subjects will undergo a review of medical history and concomitant medications, and a physical exam. The MINI International Neuropsychiatric Interview will be performed to confirm the psychiatric diagnosis. Subjects will also have a urine drug screen, urine pregnancy test, a complete blood count (CBC), complete metabolic panel (CMP), vital signs, 12-lead ECG.

Baseline visit: After the screening visit, eligible subjects will undergo: 1) vital signs; 2) efficacy assessment battery; 3) safety assessment battery; 4) blood biomarkers for inflammation and oxidative stress, including glutathione (GSH), glutathione disulfide (GSSG), high sensitivity C reactive protein (hsCRP), interleukin 6 (IL-6) and tumor necrosis factor α (TNF α).

Week 1, 2, 3 visits: Vital signs will be assessed. Treatment compliance and possible adverse effects will be evaluated. Subjects will receive one week supply of study medication. Urine drug screen will be repeated at week 2 only.

Week 4 visit: Subjects will undergo: 1) vital signs; 2) efficacy assessment battery; 3) safety assessment battery; 4) blood biomarkers for inflammation and oxidative stress, including GSH, GSSG, hsCRP, IL-6 and TNF α . Lab samples for CBC and CMP will also be collected.

Early termination visit: Subjects will undergo: 1) vital signs; 2) safety assessment battery; 3) CBC and CMP.

Statistical Analysis: A paired t-test was performed.
